Study Protocol

Tofacitinib Registry of patients with ulcerative colitis in Germany

(TOFA_{UC}-Registry)

Documentation of Tofacitinib Induction and Maintenance Therapy in conjunction with long-term outcome and predictors of response

Registry design: Investigator initiated non-interventional research (IIR)

Date: Mai 31st 2019

Principal Investigator: [name],
Gastroenterology Practice Minden,
[name],
[contact] [contact]

Co-Principal Investigator: [name]. med. [name],
Department Medicine I
University Hospital Schleswig-Holstein,
Campus Kiel,
[name]
[contact] [contact]

Sponsor/ [name]
Management: Competence Network Intestinal Diseases e.V., Kiel
[name]
[name] [contact]

Initiation: July 01th, 2019

End of recruitment: March 31st, 2021 (scheduled)

Observation period: 2 years of outcome monitoring, until March 31st, 2023

This study project is executed by "Competence Network Intestinal Diseases e.V.", Kiel.

Minden,

[name]
PI

Date

Kiel,

[name]. med. [name]
PI

Date

Kiel,

[name] (for the sponsor)
CEO Competence Network Intestinal Diseases e.V..

Date

1. Introduction

This registry on Tofacitinib and biologics (anti-integrin/anti-TNF) in the treatment of ulcerative colitis (UC) patients in Germany will extend the prospective documentation of safety issues and efficacy in induction and maintenance therapy of Tofacitinib (Xeljanz®) in addition to other biologics used in Germany with a particular interest in predictors of long-term responses and favorable disease outcome or to predict severe side effects caused by therapy with Januskinase(JAK)-inhibitors/biologics.

2. Background to the registry

The use of biologics and other immunomodulatory small molecules in UC patients is increasing; the new therapy with Tofacitinib introduces a new opportunity in UC therapy, however, up to now, no data are available on the efficacy and safety of small molecules like Tofacitinib – a JAK-inhibitor - in Germany in a real world situation. Therefore, a registry documentation of Tofacitinib (Xeljanz) is proposed to evaluate efficacy and potential side effects under real world use as well as predictors of response.

3. Aims of the registry

Primary registry objective

The aim of this registry is the prospective collection of data on the course of patients with Tofacitinib / biologics therapy in the "Real World Setting" to get insights in efficacy and safety which is relevant for the selection of the respective drugs in therapy.

The primary endpoint is steroid-free remission (remission: partial Mayo score ≤ 1 plus a bleeding subscore of 0) in the inductionphase (week 16). For this endpoint it will be only captured if there is a current use of steroids at the time of the visit. So the patient will be asked for current steroid use at time of visit at week 16 and if he has received steroids within the last 4 weeks prior to time point of the visit. As there is no common standard or definition of this endpoint in daily practice this is the most appropriate way to collect this data in non-interventional observational research.

Secondary registry objectives:

The collection of secondary objectives will be done under "Real World Conditions" to the extent that normal ongoing therapy requires normal treatment control.

1. Online documentation of safety and efficacy in induction and maintenance therapy including the occurrence of serious side effects (e.g., death, tumor, tuberculosis, severe infections, or side effects leading to hospitalization)
2. Efficacy (response: partial Mayo Score reduction of ≥ 3 accompanied by a decrease of at least 30% from baseline and remission: partial Mayo score ≤ 1 plus a bleeding subscore of 0) of induction therapy (week 8 and 16) and maintenance therapy (months 6 to 24) and efficacy (response and remission) in different subpopulations, e.g. based on a previous biologic therapy or not.
3. Obtaining health economic data in UC patients on Tofacitinib / biologics therapy (hospitalization, disability, treatment costs, quality of life, early retirement).
4. Obtaining data of the course from UC patients with a new therapy (Tofacitinib / biologics) related to treatment strategy and psychosocial impairments

Data with regard to additional registry objectives (supplementary subgroup analyzes), will only be captured in the normal routine in the course of UC-patients' treatment and in connection with routinely planned contacts at the ibd-center:

This is a non-interventional, observational registry, where patients are treated only regarding the following rules:

- The medicinal product is prescribed in the usual manner in accordance with the approved label,
- The assignment of the patient to a particular treatment has to be done in advance to and independently from the inclusion into this NIS. The decision should be only led by the medical need of the patient and pure medical decision of the treating physician. The in- and exclusion criteria for this registry will be exclusively based on the Summary of Product Characteristics (SmPC).
- The timeframes for visits are non-binding suggestions on the base of recommended timeframes in the SmPC or standard of care procedures.
- No additional diagnostic or monitoring procedures beyond respective recommendations in the SmPC or standard of care procedures will be applied to patients and epidemiological methods are used for the analysis of collected data.

The safety and efficacy of induction and maintenance therapy of Tofacitinib and other biologics are assessed in several relevant subgroups of UC patients. Most planned analyzes are descriptive:

1. Safety and efficacy of Tofacitinib in comparison with other biologics: comparison of groups with different pretreatments (e.g., biologics-naïve and biologics-experienced UC-patients or also compared to immunosuppressive drugs in pre-treatment).
2. Effects of Tofacitinib and other biologic therapies on the number of proctocolectomies and hospitalizations

3. Treatment dynamics according to the mode of treatment over time (e.g., change in proportion of Tofacitinib and first-time use of biologics in biologic naive UC patients)

4. Registry design

This is an Investigator-initiated non-randomized, non-interventional observational prospective long-term research (IIR) as part of the normal treatment of UC patients for the safety and efficacy of Tofacitinib / biologic therapies. As of 01st July 2019, UC patients who have been provided Tofacitinib / biologics for UC according the respective label by the treating physician may be prospectively included in an online database by the participating study centers by 31st March 2021.

An interim analysis is planned at the end of patients' recruitment with respect of the induction phase (week 16) for October 2021 with a first publication of the data in a peer-reviewed journal (e.g., JCC, GUT, UEG Journal).

Up to 480 patients (including about 360 UC patients with Tofacitinib and about 120 UC patients with biologics) will be included in the online documentation. A specification to the study centers regarding the group inclusion (patients treated with Tofacitinib (group 1) or a biologics (group 2)) will not be made; this means, each study center can include patients in both groups.

We assume that approximately 20-30% of Tofacitinib patients will be biologic-naïve UC patients, many of whom will represent early disease patients (< 2 years after first diagnosis).

5. Registry conduction

Data will be documented in an online registry-like database. Follow-up documentation in an abbreviated online follow-up form takes place every 6 months during the prospective registry (M6-M24) according to the normal planned clinical visits. In group 1 and 2, the induction phase, (if patient contact occurs within the framework of normal care) will be followed by up to three additional visits (W2, 8, 16) in the first three months after initiation of Tofacitinib / biological therapy. Any medication side effects are also recorded online in an AE / SAE sheet. About 15% of documented cases are monitored by in-house or on-site monitoring. In addition, in the context of the usual care patient contacts, the supervising physician carries out a prospective documentation of the course of the disease at intervals of approximately six months.

6. Selection of registry population

The diagnosis UC is made in accordance with current DGVS/ECCO UC guidelines. Patients for whom the indication of Tofacitinib / biologics therapy has been submitted for medical indication by the treating physician can be entered in the registry. The therapy decision is made by the physician, regardless of and in advance to a potential registry participation.

There are the following inclusion and exclusion criteria:

Inclusion Criteria:

- Patients with moderate to severe Ulcerative Colitis aged 18-80 years at enrollment
- Written informed consent is given

Exclusion Criteria:

- Malignant disease in history (except for non-melanoma skin cancer)
- Any contraindication according to the SmPC of the respective medication

There are two subpopulations:

1. UC-patients (age at enrollment: 18-80 years) receiving a newly introduced Tofacitinib therapy (n=360). Previous treatment(s) with biologics or immunosuppressants is (are) permitted. About 20-30% of the Tofacitinib patients will biologic-naiv.
2. UC-patients (age at enrollment: 18-80 years) receiving a newly introduced biologics therapy (n=120). Previous treatment(s) with biologics or immunosuppressants is (are) allowed.

7. Criteria for selecting participating study sites

The investigator initiated non-interventional research (IIR) is conducted at sites in hospitals or gastroenterology practice sites that have special experience in the treatment of inflammatory bowel disease. Site selection will be directed by the principal investigator.

8. Sample size calculation, Data Monitoring, Data acquisition and statistical evaluation

Sample size calculation:

The sample size calculation is based on the achievement of the primary endpoint (steroid-free remission) at the end of the induction phase. The steroid-free remission rates between a tofacitinib therapy in "real word setting" are compared with a control group in an allocation ratio of 3:1. A total drop out rate of 10% is assumed.

Basic statistical determinations:

- Two independent groups
- Comparison of two unequal ratios to each other (proportions)
- Two-sided test problem (Fisher's exact test)
- Global alpha error of 5%.
- Power 80%
- No adjustment for multiple testing

Group allocation and acceptance of securities

The steroid-free remission rate in the control group is assumed to be 0.45.

The clinically relevant odds ratio (OR) for the primary endpoint was set to at least 1.9.

This results in the following remission rates:

Group 1: IBD on Tofacitinib proportion $p_1 = 0,61$

Group 2: IBD on control proportion $p_2 = 0,45$

Sample size:

Group	Percentage	Sample size	Sample size inclusive 10% „drop out“ Rate*
Tofacitinib	75%	325	360
Control	25%	108	120
Total	100%	433	480

Note: Due to rounding, deviations may occur in the table.

Data Monitoring: A spot-monitoring with full source data verification will be carried out in 10-15% of documented using internal, trained and certified monitors. A site monitoring plan will be drawn up by the principal investigator together with the sponsor. In the induction period, there will be an additional in-house/on-site data probability check. Selected high recruiting study centers will be subjected to an additional on-site monitoring supported by external monitoring personnel. Monitoring will start in a center when at least 10 patients will be recruited.

Data acquisition will be done online on a central server (FORGA Solutions GmbH). Data transfer and evaluation is pseudonymized. Statistical evaluation will be done by FORGA Solutions, Berlin, with the support of the institutes of the principal investigators for specific additional issues and stratification with regard to the number of prior biologics therapies (an appropriate sample size analysis will be performed before each sub-analysis).

Data evaluation is also supported by the Competence Network Intestinal Diseases e.V.. The boxes in the online documentation form are equipped by input logic settings to prevent false entries. The cumulative data, especially the side effects reports, are sent by the study coordinator in a timely manner to the biologics companies funding the registry and semiannually for internal information.

Statistical evaluation will be performed by applying the descriptive methods in terms of frequency tables and statistical values, as average values, standard deviation and quantiles. As graphical methods bar diagrams will be shown with box-and-whisker-plots for quantitative data. Furthermore,

univariate significance tests and inferential statistical methods will be done supported by applicable two-sided asymptotic significance tests and confidence intervals, including chi-square test and Wilcoxon-W test and McNemar's test for comparison of dependent variables. During the analysis of evaluation criteria local significance levels of $\alpha=0.05$ will be controlled instead of global significance levels. No adjustment for multiple tests will be proceeded. Complete evaluation criteria will be exploratory analyzed with no proceeded testing of in advance formulated hypotheses. Accordingly, to these mentioned methods the obtained p-values will be interpreted in terms of Fisher's method: a p-value will be considered as a metric data and the effect is higher the smaller is the p-value. Missing data will not be replaced.

9. Duration of the registry

The registry is planned for a 3.75-year period as a longitudinal investigation. In consultation with study coordination personnel and the funding pharmaceutical company, the registry period may be extended to a longer period than 3.75 years.

10. Study flow of the registry

Starting from July 01th, 2019, patients with UC on a Tofacitinib therapy will be documented in a prospective online documentation form at the participating study sites.

The data will be documented in an online documentation form. After initial documentation at enrollment and during induction (0, 2, 8 and 16 weeks), follow-up documentation using an abbreviated online follow-up form will be requested every 6 months during the longitudinal investigation. Any drug side effects are also captured online on a side effects form.

Endpoints:

The primary endpoint is steroid-free remission (remission: partial Mayo score ≤ 1 plus a bleeding subscore of 0) in the inductionphase (week 16) phase. For this endpoint it will be only captured if there is a current use of steroids at the time of the visit. So the patient will be asked for current steroid use at time of visit at week 16 and if he has received steroids within the last 4 weeks prior to time point of the visit. As there is no common standard or definition of this endpoint in daily practice this is the most appropriate way to collect this data in non-interventional observational research.

Efficacy (response: partial Mayo Score reduction of ≥ 3 accompanied by a decrease of at least 30% from baseline and remission: partial Mayo score ≤ 1 plus a bleeding subscore of 0) of induction therapy (week 8 and 16) and maintenance therapy (months 6 to 24) and efficacy (response and remission) in different subpopulations, e.g. based on a previous biologic therapy or not.

Consecutive patients will be enrolled at the study sites, taking the organizational conditions at the

study sites into account. The main data to be documented is as follows:

1. **Baseline documentation** including demographic data, age, gender, height, weight, nicotine consumption and country of origin:
 - 1.1. History data: date of first diagnosis, involvement pattern (endoscopy and/or capsule endoscopy), extraintestinal manifestations, fistulas, strictures and past surgery.
 - 1.2. Drug history: treatments performed to date, including treatment period and any intolerances.
 - 1.3. Current state of health: symptoms, disease activity, and classification (partial Mayo Score).
 - 1.4. Current medication: documentation of current medication (including NSAIDs), including dosage to calculate drug treatment cost.
 - 1.5. Laboratory markers: documentation of existing laboratory markers like CRP, calprotectin.
 - 1.6. Data from the patient questionnaire on disease course, social impairment, mental situation and medical support.
 - 1.7. Patient quality of life questionnaire.
 - 1.8. vaccination status.

2. **Follow-up documentation** (2, 8 and 16 weeks, 6, 12, 18, 24 months; real times, which are as close as possible to these predetermined by the infusion, injection or control frequency visits in the center). Patients will not be recalled for this observation but will visit the center at these times to receive their infusion / injection / control.

In cases of acute flare or SAE an extra documentation will be triggered (flare-up documentation):

 - 2.1. Current disease findings: clinical picture (and documented endoscopic findings), disease activity (partial Mayo Score).
 - 2.2. Current medication: documentation of current medication (including NSAIDS's), including dosage to calculate cost of drug treatment.
 - 2.3. Laboratory markers: documentation of existing laboratory markers like CRP, calprotectin.
 - 2.4. Data from the patient questionnaire on disease course, social impairment, mental situation and medical care.
 - 2.5. Patient quality of life questionnaire.

3. **AE/SAE report form:** Any adverse events (AEs) or serious adverse events (SAEs) are documented promptly in a dedicated AE/SAE follow-up form. SAE trigger an extra follow up documentation.

11. Registry outline: flow chart

	Baseline documentation	Follow-up documentation	Flare-up documentation	AE / SAE report
Time in months	0	months 6, 12, 18, 24 (+/- 4 wks) (and 3 additional visits (week 2, 8, 16) in the induction therapy)		
Informed consent	√			
Inclusion criteria	√			
Exclusion criteria	√			
Demographics	√			
Case History	√			
Drug history	√			
Patient questionnaire	√	√	(√)	(√)
Current lab markers	√	√	(√)	(√)
Clinical findings	√	√	(√)	(√)
Current medication + dosage	√	√	(√)	(√)
Part. Mayo Score	√	√	(√)	-
Quality of life (EQ-5D)	√	√	(√)	-
AE/SAE-report	√	√	(√)	√
Final evaluation	√	√	√	(√)

12. Adverse events (AEs/SAEs)

Any adverse events (AEs) or serious adverse events (SAEs) are documented immediately at the study site using the AE/SAE follow-up form (SAE-reporting within 24 hours). The physician treating the patient is also obliged to report important drug side effects centrally to the medicines authority (BfArM). The relevant legal requirements (German Drug Law § 29 and 63b following enforcement of the 14th amendment to the German Drug Law) apply in terms of processing adverse drug reactions.

Documented serious adverse events (SAEs) are forwarded within 24 hours (only working days count) to the manufacturer by the documentation center (FORGA Solutions GmbH), stating the treating

documentation center. The companies are also forwarded the anonymized initials of the patient in addition to the relevant study site data in order to enable the companies to ask the study site for any necessary additional data.

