16.1 Partial Mayo Score

English version of the partial Mayo score:

Parameter	Clinical evaluation (single choice)	Score
1. Stool frequency (per day)	
normal number of stools1-2 more than normal3-4 more than normal≥ 5 more than normal	
0123
2. Rectal bleeding (indicate the most severe bleeding of the day)	
nonestreaks of blood with stool in less than half of the casesobvious blood with stools in most casesblood alone passes	
0123
3. Physician's global assessment	
normalmild diseasemoderate diseasesevere disease	
0123

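### Remission and response at months 6 to 24 rest on the partial Mayo score alone, with no rule for patients who have had a proctocolectomy; this can bias the maintenance rates upward

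*Protocol*

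**What the plan says.** Secondary objective 2 in protocol section 3, repeated under the endpoints in section 10, sets both efficacy rules. Remission is "partial Mayo score ≤ 1 plus a bleeding subscore of 0) of induction therapy (week 8 and 16) and maintenance therapy", running through months 6 to 24. Response is "partial Mayo Score reduction of ≥ 3 accompanied by a decrease of at least 30% from baseline". Neither rule carries a condition about surgery or about still being on the drug.

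Section 16.1 builds the score from three items, each scored 0 to 3: "1. Stool frequency (per day"), graded against the patient's normal number; "2. Rectal bleeding (indicate the most severe bleeding of the day"); and the physician's global assessment.

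Surgery is foreseen. Item 2 of the planned analyses in section 3 reads "Effects of Tofacitinib and other biologic therapies on the number of proctocolectomies and hospitalizations". That count is not linked to remission or response.

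The flow chart in section 11 ticks the partial Mayo score for the follow-up visits, and no section ends follow-up at surgery. Section 10 lists past surgery in the baseline history (item 1.1) but names no surgery item at follow-up (items 2.1 to 2.5). On missing values, section 8 states: "Missing data will not be replaced".

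**The concern.** Once colon and rectum are removed, the score no longer measures what the drug does. The bleeding item becomes 0 because the organ is gone, and a well patient with a stoma may also receive low values on the other two items. The written rules then have two ways of not recording a failure: the patient is scored low and qualifies, or the patient is not scored and contributes nothing.

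The second way is realistic. Section 10 says patients are not called in specially; they are documented when they attend for an infusion, injection or check-up. Someone whose drug was stopped after surgery may have no such visit.

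At stake is the long-term comparison between tofacitinib and biologics, which section 3 says is meant to inform the choice of drug. If one group has more surgery, its remission rate can be lifted more, so the efficacy comparison can move against the colectomy count reported beside it.

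**Working it through.** **What the plan offers.** There is no stated figure to reproduce on this point: the protocol gives neither a colectomy rate nor a remission rate at months 6 to 24. The only rates are the week-16 planning values in section 8: 0.45 for control and an odds ratio of 1.9. These give odds of 1.9 × 0.45/0.55 = 1.5545 and a rate of 1.5545/2.5545 = 0.6085, printed as 0.61. They are borrowed below as illustrations only.

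**Step 1: which scores qualify once bleeding is 0.** Stool frequency and global assessment each run 0 to 3, giving 4 × 4 = 16 combinations.
- Remission needs stool + global assessment ≤ 1. Three combinations qualify: (0,0), (0,1) and (1,0). The other 13 fail, including every one with either subscore at 2 or more.
- Response is easier. With bleeding 0 and global assessment 0, a baseline of 6 or more qualifies even at the maximum stool subscore of 3: from 6 to 3 is a fall of 3 points and 50%.
- From any baseline of 4 to 9, a post-surgery score of 0 or 1 meets the response rule (from 4 to 1 is a fall of 3 points and 75%).

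**Step 2: effect on the rate.** Let R be the share of all patients in remission when operated patients count as failures, and c the share operated on by the visit.
- Counted as failure: R.
- Unscored and left out: R/(1 − c).
- All scored as remission: R + c. This is an upper bound. If only a fraction f of them score as remission and all are scored, the rate is R + f·c, which returns to R at f = 0.

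With R = 0.45 and c assumed:

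| c (assumed) | Failure | Left out | All scored as remission |
|---|---|---|---|
| 2% | 0.450 | 0.45/0.98 = 0.459 | 0.470 |
| 5% | 0.450 | 0.45/0.95 = 0.474 | 0.500 |
| 8% | 0.450 | 0.45/0.92 = 0.489 | 0.530 |

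The shift is +0.9 to +3.9 points if left out, and at most +2 to +8 points if scored.

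**Step 3: effect on a comparison.** Assume colectomy in 3% of one group and 8% of the other.
- Equal true rates of 0.45. Left out: 0.45/0.92 − 0.45/0.97 = 0.489 − 0.464 = 0.025. All scored as remission: 0.53 − 0.48 = 0.05. Both favour the group with more surgery.
- True rates 0.61 and 0.45 (16 points), with 3% in the first group and 8% in the second. Left out: 0.61/0.97 − 0.45/0.92 = 0.629 − 0.489 = 0.140. All scored as remission: 0.64 − 0.53 = 0.11.

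The protocol does not indicate which group would have more surgery, so the direction of any distortion between groups is open.

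**The case against.** **This belongs in the SAP.** Classifying patients after surgery, a drug switch or death is commonly left to the SAP, which may exist and is not shown. That would answer a complaint about missing detail alone. It does not fully answer this one, because the protocol itself fixes both the score-only definition and the missing-data rule. An SAP that follows them literally inherits the problem; one that counts surgery as failure must add a condition to the protocol's definition.

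**The rules do not force a wrong answer.** A reader might infer that every operated patient is either scored a success or dropped. The documents do not support that: 13 of the 16 combinations in step 1 are non-remission under the rule as written. This part stands, and it limits the claim to a possible bias. The result then depends on how a site scores items that no longer apply.

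**The drop path is a general missing-data matter.** Section 8 rules out replacement but does not say that unscored patients leave the denominator, and the same wording touches anyone lost to follow-up. Both are fair, so the drop figures assume an observed-case analysis. Colectomy still differs from ordinary loss: the event is known, and classifying it needs no imputation.

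**The size is assumed and modest.** The colectomy rates, the 3% versus 8% split and the use of week-16 rates at month 24 are all assumptions. The standard error of a group difference at 325 and 108 patients and a rate of 0.45 is √(0.45 × 0.55 × (1/325 + 1/108)) = 0.055, so shifts of 2.5 to 5 points lie below one standard error. This stands. A systematic shift does not average out as sampling error does, but it is not large here.

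**The endpoint is secondary.** Section 3 calls most analyses descriptive, section 8 treats the criteria as exploratory, and the surgery count is planned in its own right. This also stands, and limits the weight of the point.

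**Conclusion.** The concern holds as a possible upward bias in remission and response at months 6 to 24. The protocol expects proctocolectomies, defines success by a score that surgery itself alters, and replaces no missing values. An operated patient can therefore count as a success or supply no failure; non-remission is recorded only if the stool and global-assessment items happen to be scored high enough.

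The size cannot be derived. With 2% to 8% colectomy and a remission rate of 0.45, both assumed for the maintenance period, it is about +0.9 to +3.9 points under observed-case analysis. The +2 to +8 points for scored patients is a ceiling, since it takes every operated patient to score as remission.

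Three stronger readings are not supported:
- Surgery is not the worst outcome recorded. Secondary objective 1 in section 3 covers "occurrence of serious side effects (e.g., death, tumor, tuberculosis, severe infections, or side effects leading to hospitalization").
- The bias is not certain, for the reason given in step 1.
- No separate bias is shown for the primary endpoint, steroid-free remission at week 16, and the planned sample size is unaffected.

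The point is worth correcting because the remedy is specific and cheap; it does not undermine the registry's main analysis.

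**What to change.** In sections 3 and 10, add to the remission and response definitions a sentence to this effect: for the analysis, a patient who has had a (procto)colectomy counts as non-remission and non-response at that visit and all later visits, whatever the partial Mayo score and also when it is missing, and stays in the denominator. Add the date of surgery to the follow-up documentation in section 10.

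This is a rule for classifying data and changes nothing in patient care. The primary endpoint uses the same remission rule, so the sentence would carry over to week 16 for consistency.

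The cost is one sentence, one date field and one derivation flag. A colectomy would ordinarily meet the hospitalisation criterion in section 12.1, so much of the information should already reach the registry through the SAE form. The downside is slightly less favourable reported rates.

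### The calendar change in the tofacitinib share among enrolled patients (Section 3, planned analysis 3) cannot be relied on as a measure of treatment uptake, because the protocol does not say whether the 3:1 target or consecutive enrolment sets the mix

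*Protocol*

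**What the plan says.** Section 3 (Aims of the registry) introduces three subgroup analyses with the remark "Most planned analyzes are descriptive". The third concerns treatment dynamics over time, and its only example is the "change in proportion of Tofacitinib and first-time use of biologics in biologic naive UC patients".

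Section 4 (Registry design) sets the intended composition: "Up to 480 patients (including about 360 UC patients with Tofacitinib and about 120 UC patients with biologics) will be included". Section 6 repeats 360 and 120 as the sizes of the two subpopulations. Section 8 shows their origin: a 3:1 allocation and a 75%/25% table in the sample size calculation for week-16 steroid-free remission.

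Other statements bear on how that composition arises:

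- Section 4 says that centers get no specification about group inclusion and that each may enrol into both groups.
- Sections 3 and 6 say that treatment is chosen before, and independently of, registry inclusion.
- Section 10 says "Consecutive patients will be enrolled at the study sites", qualified by the organizational conditions at the sites.
- Section 4 words inclusion as a possibility (patients may be included), not as a requirement.

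The protocol describes no record of all tofacitinib and biologic starts at the sites, and no rule for what happens when one group reaches its planned size.

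**The concern.** A treatment share followed over calendar time needs a denominator: all patients who start one of the treatments. Here the only denominator described is the patients who were enrolled. Their planned mix comes from a power calculation, not from prescribing data.

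If the mix is managed towards 3:1, a calendar trend in the enrolled share shows when each group filled and how readily sites registered each drug. The result could display a shift that did not happen, or hide one that did. Section 15 plans regular publication while the registry is running, so such a figure could be read as evidence on tofacitinib uptake in Germany.

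**Working it through.** **1. Where 360/120 comes from.** Inputs from Section 8: control rate 0.45, odds ratio 1.9, two-sided alpha 5%, power 80%, ratio r = 3, dropout 10%.

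- Tofacitinib rate: odds = 1.9 × 0.45/0.55 = 1.555, so p1 = 1.555/2.555 = 0.609. The plan gives 0.61.
- Control group without continuity correction, with p̄ = (3 × 0.61 + 0.45)/4 = 0.57 and d = 0.16: n = [1.96·√((1 + 1/3)·0.57·0.43) + 0.842·√(0.61·0.39/3 + 0.45·0.55)]² / 0.16² = 100.2. This rounds up to 101 + 303 = 404, short of the plan's 433.
- With continuity correction, which approximates Fisher's exact test: n′ = (n/4)·[1 + √(1 + 2(r + 1)/(r·n·d))]² = 108.4, and 3 × 108.4 = 325.1. The plan has 108 and 325. Rounding each group up gives 109 + 327 = 436, within 1% of 433.
- Exact Fisher power at 325/108 is 81.5%.
- Dropout: 325/0.9 = 361 and 108/0.9 = 120. The plan has 360 and 120.

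The figures reproduce. They depend only on remission rates and the chosen ratio; no prescribing share enters.

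**2. What the targets imply.** If they are met, the overall enrolled tofacitinib share is 360/480 = 75%, whatever the sites prescribe. Let k be the fraction of tofacitinib starters enrolled divided by the fraction of biologic starters enrolled. Then enrolled odds = prescribing odds × k, and a 75% share (odds 3) needs k = 3/(prescribing odds). The documents give no prescribing share, so a range is assumed:

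| Assumed tofacitinib share of starts | k needed for 75% enrolled |
|---|---|
| 10% | 27 |
| 20% | 12 |
| 30% | 7 |
| 50% | 3 |
| 75% | 1 |

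Consecutive enrolment of everyone (k = 1) gives 360/120 only if the sites' own share happens to be 75%.

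**3. No change in practice.** Assume 1:1 starts throughout and a cap on each group (neither is in the protocol). The first 240 enrolled are 120 + 120, a share of 50%. The remaining 240 are all tofacitinib, a share of 100%. Overall: 360/480 = 75%. A 3:1 quota kept throughout would show a flat 75%.

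**4. One true trend under four recruitment rules.** Assume the tofacitinib share of starts rises evenly from 10% to 30% over the 7 quarters of recruitment (mean 20%).

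| Recruitment rule | Enrolled share over time |
|---|---|
| Consecutive, no caps | 10% to 30% (correct), but about 96 tofacitinib and 384 biologic patients |
| Constant k = 12 | 57% to 84% |
| Group caps, assumed 250 eligible per quarter | 25/(25 + 120) = 17% in quarter 1, then 100% |
| 3:1 quota in each quarter | 75% throughout |

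In the constant-k row the level is wrong but the odds ratio from first to last quarter is right: (0.30/0.70)/(0.10/0.90) = 3.86 in practice, and (12 × 0.30/0.70)/(12 × 0.10/0.90) = 5.14/1.33 = 3.86 among the enrolled. In the last two rows the trend itself is lost.

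**The case against.** The strongest reply is that the protocol describes neither caps nor quotas. The targets are approximate, sites receive no group specification, treatment is chosen independently of inclusion, and enrolment is to be consecutive. On that reading the mix would follow practice at the sites. The item is also one example in a mostly descriptive list, the document never claims to estimate prescribing shares, and the wording could cover treatment changes during follow-up, when current medication is recorded at each visit.

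Much of this stands. A reader might infer that the enrolled share necessarily follows the targets and not prescribing, or that the change in share can never be learned from this registry. The documents support neither. No rule closes a full group, and with truly consecutive enrolment, or a selection ratio constant over time, the odds-ratio trend is preserved.

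The reply does not rescue the analysis as planned, because the protocol secures neither condition. Consecutive enrolment is qualified by site organization, inclusion is optional, and k cannot be checked without a count of all starts. If consecutive enrolment does govern, the 3:1 mix on which the sample size rests is not assured.

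A further objection is that the biologic-naive share within each group also uses enrolled patients. That is correct. With 1:1 starts at a constant rate and caps (again assumed), the biologic group would fill after 120/360 of the 21-month recruitment period, about 7 months, and no trend could be shown for it afterwards. The fix takes account of this.

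**Conclusion.** The concern holds in a limited form. The protocol plans a 3:1 mix derived from a power calculation and also consecutive enrolment with no group specification. Both cannot be guaranteed, and it does not say which governs. With optional inclusion and no denominator of all starts, the calendar change in the enrolled tofacitinib share cannot be relied on as a measure of treatment uptake.

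The size depends entirely on the unstated recruitment rule: with no change in practice, the display can run from 50% to 100% or stay flat at 75%. These figures rest on an assumed 1:1 start ratio and on assumed caps or quotas; they are illustrations, not predictions. The matter concerns one example within a descriptive secondary analysis and is worth correcting because the remedy is nearly free.

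**What to change.** Limit item 3 of the planned analyses to within-patient treatment sequences over 24 months: persistence, stopping, and switching and to which drug. The medication already recorded at follow-up supports this, and it does not depend on the enrolment mix.

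If a calendar description is wanted, add the share of biologic-naive patients within each group by quarter of enrolment. Restrict it to quarters in which that group is open to enrolment, and describe it as a feature of the enrolled cohort.

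Remove the calendar change in the tofacitinib proportion among enrolled patients, and state that the registry does not estimate prescribing shares. Section 4 or 10 should also say whether the 3:1 target or consecutive enrolment governs, and what happens when one group reaches its planned size.

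The cost is a few sentences and one descriptive secondary result. No new data are needed, and the primary endpoint is unaffected.
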